### Table 3: Schedule of Activities (Extended Treatment Period)

- b If a participant is discontinued from the study during the ETP, an ED Visit will be performed, and then an EOS Visit will be performed 30 (±2) days after the last dose of study intervention.
- c Evaluation of CD must be performed as soon as possible, within 48 h of notification to the Investigator of symptom onset. If CD occurs between scheduled visits, only the assessments for the CD Visit are needed. If CD occurs on a scheduled visit, all scheduled assessments should be performed for that visit as well as for the evaluation of CD. Additional evaluation visits may be scheduled at the discretion of the Investigator.
- d Ensure kit and lot number are recorded on the drug accountability log.
- e Dosing is by mouth bid throughout the ETP.
- f Participants will receive newly dispensed study intervention at Week 34 and the first dose will be administered during this visit. The participant will then continue at home dosing per protocol.
- g MG assessments should be performed at approximately the same time of day by a properly trained Clinical Evaluator (preferably the same evaluator). The MG-ADL should always be performed first, followed by the QMG.
- Note: A Clinical Evaluator may be a neurologist, neurologist in training, or delegated member of the investigational site staff who has been certified in administering the assessments.
- h The QMG assessment should be performed by a properly trained Clinical Evaluator (preferably the same evaluator) throughout the study. If a participant is taking a cholinesterase inhibitor, the dose must be withheld for at least 8 h prior to the assessment and, whenever possible, the time from the last dose to the QMG assessment should be kept similar between visits.
- i The MG-ADL is required to be performed first, followed by the QMG. The MG-ADL assessment should be performed by a properly trained Clinical Evaluator (preferably the same evaluator) throughout the study. The recall period for MG-ADL is the preceding 7 days or since the last visit if the visit interval is less than 7 days. The MG-ADL will be assessed by phone at Weeks 9, 10, 11, 13, 14, and 15.
- j C-SSRS will be assessed Since Last Visit.
- k To be performed, if necessary, on the basis of the participant's health status and the clinical judgment of the Investigator.

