1. INTRODUCTION

This statistical analysis plan (SAP) describes the statistical methods for analyzing data for the protocol titled "A Phase 2, Randomized, Double-blind, Placebo-Controlled, Multicenter Study to Evaluate the Efficacy and Safety of ALXN2050 in Adult Participants With Generalized Myasthenia Gravis." Standard data presentation instructions and table, figure, and listing specifications are contained in the data presentation plan in a separate document.

Throughout the study, 3 analyses will be performed with different data cutoff and emphasis as follows:

- Analysis 1 (Week 8): The first analysis will be performed after the last randomized participant has completed the Primary Evaluation Period (PEP) or discontinued study treatment during the PEP. Specifically, this includes the PEP data for all participants, as well as the Extended Treatment Period (ETP) and Open-Label Extension (OLE) Period data, up to the data cutoff date or early discontinuation date, whichever occurs earlier. The primary, secondary, and select exploratory efficacy endpoints; safety endpoints; pharmacokinetic (PK) and pharmacodynamic (PD) endpoints; and baseline information (demographics and disease characteristics) will be analyzed. Biomarker endpoints will be analyzed if available at the first analysis.
- Analysis 2 (Week 34): The second analysis will be performed after the last randomized participant has completed the ETP or discontinued study treatment before the completion of the ETP. Specifically, this includes the PEP and ETP data for all participants, as well as the OLE Period data, up to the data cutoff date or early discontinuation date, whichever occurs earlier . Exploratory efficacy endpoints, additional safety, PK/PD, and biomarker data will be analyzed.
- Final analysis: The final analysis will be performed at the end of study (EOS) when all participants have completed the study or discontinued treatment early. The data in scope include efficacy, available PK/PD, biomarker, and safety data other than adverse events (AEs) of the OLE Period and aggregated AE data throughout the study, as defined in Section 5.9.

| Objectives | Endpoints |
|--|---|
| Primary | |

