5.3.1. Primary Endpoint

The primary endpoint is the proportion of participants with an MG-ADL total score reduction of ≥ 2 points from the Baseline in any 4 consecutive weeks during the first 8 weeks and who did not receive rescue therapy. To compute this, change from Baseline in the MG-ADL total score at each post-Baseline Visit of the first 8 weeks will be derived, where baseline is defined as the last nonmissing assessment prior to the first dose of study intervention. In general, this baseline assessment will be the Day 1 assessment. If the Day 1 assessment is missing, the latest observation during the Screening Period, where available, will be used as the baseline assessment.

Participants who discontinued early without achieving an MG-ADL total score reduction of ≥ 2 points from the Baseline in any 4 consecutive weeks during the first 8 weeks will be considered as nonresponders. Participants who received rescue therapy anytime during the first 8 weeks will be considered as nonresponders.

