5.5.1.1. Dual Responder in MG-ADL and QMG

The FAS will be used for this analysis.

Responder is defined as participants with both an MG-ADL total score reduction of ≥ 2 points and a QMG total score reduction of ≥ 3 points in any 4 consecutive weeks during the first 8 weeks and who did not receive rescue therapy. The number and proportion of responders will be summarized by treatment group. The exact (Clopper-Pearson) 90% CI for each treatment group will be presented. The differences in proportions between each of the ALXN2050 dose groups (180 mg bid or 120 mg bid) and the placebo group will be presented, along with 2-sided 90% CIs using the Chan and Zhang method (Chan, 1999). The same intercurrent event handling approach will be followed as specified in the primary analysis of the primary endpoint in Table 1.

5.5.1.2. Proportion of Participants With 2-Point Improvement in the MG-ADL Total Score for 4 Consecutive Weeks and Who Did Not Use Rescue Therapy

The FAS will be used for this analysis.

This analysis includes MG-ADL data of the first 8 weeks (Groups 1, 2, and 3) and Week 8 to 16 data for Groups 3a and 3b participants who have completed Week 16 assessment or discontinued prior to Week 16 by the data cutoff date.

The proportion of participants with at least a 2-point improvement in the MG-ADL total score for 4 consecutive weeks (measured from Day 1 [PEP baseline] to Week 8 for Groups 1, 2, and 3 and from Week 8 [ETP baseline] to Week 16 for Groups 3a and 3b) and who did not receive any rescue therapy will be summarized. The exact (Clopper-Pearson) 90% CI for each group will be presented. Summaries using the PEP and ETP baselines will be both presented for Groups 3a and 3b. The same intercurrent event handling approach will be followed as specified in the primary analysis of the primary endpoint in Table 1.

For Groups 3a and 3b, this endpoint will be summarized in a shift table presenting the shift in responder status from the first 8 weeks to Weeks 8 to 16 (using the PEP and ETP baselines separately for Week 8 to 16 responder status). The observed frequencies and percentages, together with an exact (Clopper-Pearson) 90% CI for the true percentage of responders, will be presented for the first 8 weeks and Weeks 8 to 16 separately. The difference in percentages of responders (Weeks 8 to 16 [first 8 weeks]) and corresponding 90% CI for the true difference will also be presented for each group.

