5.5.2. Tertiary/Exploratory Endpoints Analyses at Analysis 2 (Week 34)

This section describes all analyses to be performed at the second analysis when all participants have completed the first 34 weeks of treatment or have discontinued treatment. All exploratory endpoint analyses will be performed on the FAS population, unless specified otherwise.

5.5.2.1. Proportion of Participants With 2-Point Improvement in the MG-ADL Total Score for 4 Consecutive Weeks and Who Did Not Use Any Rescue Therapy

This analysis includes MG-ADL data of the first 8 weeks (Groups 1, 2, and 3) and Week 8 to 16 data for all Group 3a and 3b participants.

The analysis described in Section 5.5.1.2 will be repeated with all available data as of the data cutoff date.

5.5.2.2. Change From Baseline in the MG-ADL Total Score at Week 8 for Group 1, 2, and 3 and From Weeks 8 to 16 for Groups 3a and 3b

This analysis includes MG-ADL data of the first 8 weeks (Groups 1, 2, and 3) and Week 8 to 16 data for all Group 3a and 3b participants.

The analysis described in Section 5.5.1.3 will be repeated with all available data as of the data cutoff date.

5.5.2.3. Change From Baseline in the MG-ADL Total Score at Week 26 for Groups 1 and 2

This analysis will be covered in the analysis in Section 5.5.2.4.

5.5.2.4. Change From Baseline in the MG-ADL Total Score at Week 26 for Groups 1 and 2 and From Weeks 8 to 34 for Groups 3a and 3b

This analysis includes MG-ADL data of first 8 weeks (Group 1, 2, and 3) and Week 8 to 34 data for Group 1, 2, 3a, and 3b participants.

Change from Baseline in the MG-ADL total score at Week 26 for Groups 1 and 2 and change from Baseline in the MG-ADL total score at Week 34 for Group 3a and 3b will be summarized. Change from Baseline in the MG-ADL total score by study visit up to Week 34 and treatment group will be summarized.

Summaries using the PEP and ETP baselines will be both presented for Groups 3a and 3b.

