1.2. Changes From Analyses Specified in the Previous Version of the SAP

- Primary endpoint: primary endpoint analyses will be performed as described in the SAP Amendment Version 1.0 Section 5.3.2. Sensitivity and supplementary analyses will not be performed.
- Secondary efficacy endpoints: only change from baseline in the QMG total score and change from baseline in the MG-ADL total score as described in the SAP Amendment Version 1.0 Section 5.4.1.1 and Section 5.4.1.3 (excluding the trend analysis to detect dose-response trend) will be performed. Descriptive summary of absolute and change from Primary Evaluation Period (PEP) baseline in MG-ADL and QMG total score will tabulate study visits through the entire study. Supplementary analyses will not be performed.
- PK/PD: PK parameter will not be reported as described in the SAP Amendment Version 1.0 Section 5.7.1.3. Population PK and exposure-response analysis will not be performed as described in the SAP Amendment Version 1.0 Section 5.7.3. All other PK/PD analyses will be performed.
- Biomarker: biomarker analysis will not be performed.
- Safety: All safety analyses will be performed as planned, as described in the SAP Amendment Version 1.0 Section 5.6 with all data collected until the end of study.
- No exploratory endpoint analyses will be performed.
- All other analyses (e.g., demographic, baseline disease characteristics, MG/non-MG medications/therapies, protocol deviation, etc), if not mentioned above, will be performed as planned.

Study exposure and adverse event data summaries will include the following two sets of analyses: (1) summary of the PEP data by Group 1, 2, 3; (2) summary of the ALXN2050 Treated Period data by Group 1, 2, 3a, 3b. Per-protocol Set and Re-randomized Set will be removed.

Medication summaries by treatment group and overall using the number and percentage of participants will be presented by WHO-DRUG Anatomical Therapeutic Chemical Level 3 class code and by WHO-DRUG generic name.

All planned listings other than the ones for exploratory biomarker endpoints will be produced.

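### At Analysis 1, placebo participants switched to ALXN2050 less than 8 weeks before the cutoff enter the Week 8 to 16 responder summary only if they discontinue, which biases it slightly downward

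*SAP*

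**What the plan says.** SAP 5.5.1.2 defines the Analysis 1 summary of 2-point MG-ADL responders over 4 consecutive weeks. For the switched placebo arm it takes Week 8 to 16 data from "Groups 3a and 3b participants who have completed Week 16 assessment or discontinued prior to Week 16 by the data cutoff date". The section then calls for an exact 90% interval for each group, a shift table against the participant's own placebo period, and a within-group difference with its interval.

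Three other provisions fix how this works:

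- **Timing.** SAP Section 1: "The first analysis will be performed after the last randomized participant has completed the Primary Evaluation Period (PEP) or discontinued study treatment during the PEP".
- **Discontinuation.** SAP 5.5.1.2 adopts the primary-endpoint rule: "The same intercurrent event handling approach will be followed as specified in the primary analysis of the primary endpoint in Table 1". Under SAP 5.3.1 and Table 1, the nonresponders are "Participants who discontinued early without achieving an MG-ADL total score reduction of ≥ 2 points from the Baseline in any 4 consecutive weeks", together with anyone given rescue therapy.
- **Assessments.** Protocol Table 3: "The MG-ADL will be assessed by phone at Weeks 9, 10, 11, 13, 14, and 15", with clinic visits at Weeks 12 and 16. MG-ADL is therefore weekly, and a 4-week response cannot be complete until about Week 12.

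At Analysis 2, SAP 5.5.2.1 uses "Week 8 to 16 data for all Group 3a and 3b participants". For the final study report, Section 1.2 of the later SAP addendum states: "No exploratory endpoint analyses will be performed".

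**The concern.** A placebo participant re-randomised fewer than 8 weeks before the cutoff cannot yet have completed Week 16. The first limb of the inclusion rule is closed to that person, and only the second, discontinuation, remains. Of two participants re-randomised on the same late date, the one who stops treatment is counted and the one who continues is not, even if the second is already improving.

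Entry to the denominator thus depends on an event closely tied to the outcome. Someone who stops in the first weeks after the switch has had little or no time to build 4 consecutive weeks of response, so nearly all the late additions are nonresponders. At stake is the apparent response rate of the switched participants on each dose at Analysis 1, and the comparison with their own placebo period that is built on it.

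**Working it through.** **Plan's own figure.** The SAP gives no figure for this summary. The response rates used below (60%, 45%, 25%) are the sample-size assumptions in SAP Section 3. The power stated there, about 80% for 60% versus 25% with 27 per arm, reproduces as 81.2% by exact enumeration of a two-sided Barnard test at 0.10.

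**Inputs from the documents**

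- 70 participants randomised 2:1:2, so 70 × 2/5 = 28 on placebo, and 28/2 = 14 in each of Groups 3a and 3b (SAP 1.2).
- Full follow-up for this endpoint is 8 weeks after the switch (Week 8 to Week 16).

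**Assumptions not in the documents**

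- Uniform accrual over A = 26 to 104 weeks.
- Constant dropout hazard, with d = 5% to 20% leaving per 8 weeks.
- Response p = 60%, 45% or 25% in the absence of dropout, first reachable 4 to 8 weeks after the switch.
- Cutoff at the last participant's Week 8.

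**Formula**

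- Share of participants switched less than 8 weeks before the cutoff: f = 8/A.
- Share both recent and already discontinued: q = f × [1 − d/(−ln(1 − d))].
- r_opp is the response rate among those with a full 8 weeks of opportunity. r_rec is the rate among the recent discontinuers.
- Reported rate minus r_opp = q(r_rec − r_opp)/(1 − f + q).

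**Worked case: A = 26, d = 20%, p = 60%**

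- f = 8/26 = 0.308.
- q = 0.308 × (1 − 0.2/0.2231) = 0.308 × 0.104 = 0.032.
- Simulated r_opp = 0.508 and r_rec = 0.050.
- Bias = 0.032 × (0.050 − 0.508)/(0.692 + 0.032) = −0.020, or −2.0 points.

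**Simulation** (1,000,000 participants per scenario)

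| Accrual (weeks) | Dropout per 8 weeks | p | r_opp | Reported | Bias (points) |
|---|---|---|---|---|---|
| 26 | 20% | 60% | 0.508 | 0.488 | −2.02 |
| 26 | 10% | 60% | 0.555 | 0.544 | −1.10 |
| 52 | 20% | 45% | 0.381 | 0.375 | −0.63 |
| 52 | 10% | 60% | 0.555 | 0.551 | −0.45 |
| 104 | 20% | 60% | 0.509 | 0.505 | −0.40 |
| 104 | 5% | 25% | 0.240 | 0.239 | −0.04 |

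The bias was downward in all 36 scenarios and below 1 point in 33. Inclusion by opportunity matched the full-cohort rate throughout. Recent discontinuers had response rates of about 2% to 6%, against 21% to 58% in the full cohort. The expected number of them in a group of 14 was 0.03 to 0.45.

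**Faster accrual.** At 6 placebo re-randomisations a month (28/6 = 4.7 months in all), 20% dropout, 50% response among those who stay and every dropout counted as a failure, the reported rate was 37.0% against 39.7%, a gap of 2.7 points. Crediting those who respond before leaving lowers this only slightly, to about 2.6.

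**One realised group**

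- Ten eligible, five responders: 5/10 = 50%. One recent dropout gives 5/11 = 45%.
- Fourteen in the group, four of them recent, six responders among the other ten: 6/10 = 60%. One recent dropout gives 6/11 = 54.5%, and two give 6/12 = 50%.

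**Within-group difference.** A recent discontinuer without a response contributes either 0 or −1 to the difference between Weeks 8 to 16 and the placebo period. If the other participants show a positive difference, adding such people lowers it.

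**The case against.** The strongest objection is size. With 7 responders in 14, the exact 90% interval runs from about 26% to 74%, so an expected bias of 2 points or less is lost in the imprecision. The 2.7-point figure needs about 15 randomisations a month across all arms (6 × 5/2). The dates in the documents suggest slower accrual: an April 2021 protocol, country amendments still issued in mid-2022, and a Week 8 SAP addendum in December 2023. At 1.2 placebo re-randomisations a month (28/1.2, about 23 months), the bias is only 0.1 to 0.4 points. All of this stands, and it makes the point minor.

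The rule is also not isolated. SAP 5.5.1.3 tabulates MG-ADL change by visit for all data to the cutoff, so the scores of ongoing recent entrants do appear at Analysis 1. The SAP does not fix the gap between the last Week 8 visit and the cutoff, and a longer gap would shrink the bias. These points soften the effect but leave the responder summary as it is.

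A reader might infer three stronger things that the documents do not support:

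- **Recent entrants count only if they fail.** They count only if they discontinue. SAP 5.3.1 leaves someone who met the 4-week response and then stopped as a responder. Nor are all ongoing participants excluded, since those past Week 16 are in. Ongoing recent entrants already given rescue are left out too, so some known failures are also missing.
- **The bias affected the development decision.** The addendum attributes termination to lack of efficacy relative to placebo at Week 8. This summary has no concurrent placebo, SAP 5.5 plans no formal testing of it, and no section ties it to a decision.
- **Analysis 2 repairs it.** That was the plan, but the addendum drops exploratory endpoints from the single final report.

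**Conclusion.** The inclusion rule in SAP 5.5.1.2 is wrong as written, and the error is minor. Followed literally, it selects recent entrants on discontinuation and biases the Week 8 to 16 responder proportion for Groups 3a and 3b downward, along with the interval, shift table and difference derived from it. Direction and mechanism follow from the text alone.

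The size rests on assumed accrual and dropout: about 0.04 to 2 points in expectation, usually under 1, and about 2.7 if accrual was much faster. In a group of 10 to 14, a single extra early dropout moves the observed rate by about 5 points.

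The primary endpoint is untouched. The separate SAP addendum for the Week 8 analysis is not among the documents, so whether this rule was actually applied at Analysis 1 cannot be settled here. The point matters for any Analysis 1 output already produced under it, and for reuse of the wording.

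**What to change.** Replace the inclusion condition in SAP 5.5.1.2 with:

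> Groups 3a and 3b participants whose scheduled Week 16 date (first ETP dose plus 8 weeks, with the visit window) falls on or before the data cutoff, whether or not they discontinued.

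Inclusion then depends only on time since the switch, and the Table 1 handling of discontinuation and rescue can stay as it is.

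The cost is one sentence. A few recent discontinuers leave the Analysis 1 denominator. So might a participant who completed Week 16 within days of the cutoff but whose ±3-day window had not yet closed. Because the final report no longer carries this endpoint, those participants would not reappear in a later responder summary. If an Analysis 1 table was already produced under the existing rule, a footnote giving the number of recent discontinuers in each group would let readers judge the effect.

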5.5.1.6. Incidence of Clinical Deterioration of gMG Over Time

The FAS will be used for this analysis.

A detailed definition of clinical deterioration is in Section 6.3.1. Incidence of clinical deterioration of gMG during the first 8 weeks will be summarized by Groups 1, 2, and 3. The number and percentage of participants experiencing clinical deterioration, the total number of clinical deteriorations, and the difference in percentage of participants experiencing clinical deterioration between each ALXN treatment arm and placebo arm (along with 90% CIs) will be presented. Exact (Clopper-Pearson) 90% CIs for the true proportions will be presented.

5.5.1.7. MGFA-PIS at Week 8

The FAS will be used for this analysis.

A summary of the MGFA-PIS will be presented by treatment group and study visit (including Week 8 and all visits up to the data cutoff date), showing the number and percentage of participants in each category (ie, improved, unchanged, or worsened) and the number and percentage of participants who achieved MMs. The difference in the percentage of participants achieving "improved" status between each ALXN treatment arm and placebo arm will be presented, along with 90% CIs for the PEP study visits. The difference in the percentage of participants achieving MMs between each ALXN arm and placebo arm will be presented, along with 90% CIs.

5.5.1.8. Proportion of Participants Who Received Rescue Therapy Over Time

The FAS will be used for this analysis.

Proportion of participants who received rescue therapy during the first 8 weeks will be summarized by Group 1, 2, and 3. The number and percentage of participants who received rescue therapy, as well as the number of clinical deteriorations requiring rescue therapy, will be presented. Exact (Clopper-Pearson) 90% CIs for the true proportions will be presented.

5.5.2. Tertiary/Exploratory Endpoints Analyses at Analysis 2 (Week 34)

This section describes all analyses to be performed at the second analysis when all participants have completed the first 34 weeks of treatment or have discontinued treatment. All exploratory endpoint analyses will be performed on the FAS population, unless specified otherwise.

5.5.2.1. Proportion of Participants With 2-Point Improvement in the MG-ADL Total Score for 4 Consecutive Weeks and Who Did Not Use Any Rescue Therapy

This analysis includes MG-ADL data of the first 8 weeks (Groups 1, 2, and 3) and Week 8 to 16 data for all Group 3a and 3b participants.

The analysis described in Section 5.5.1.2 will be repeated with all available data as of the data cutoff date.

5.5.2.2. Change From Baseline in the MG-ADL Total Score at Week 8 for Group 1, 2, and 3 and From Weeks 8 to 16 for Groups 3a and 3b

This analysis includes MG-ADL data of the first 8 weeks (Groups 1, 2, and 3) and Week 8 to 16 data for all Group 3a and 3b participants.

The analysis described in Section 5.5.1.3 will be repeated with all available data as of the data cutoff date.

5.5.2.3. Change From Baseline in the MG-ADL Total Score at Week 26 for Groups 1 and 2

This analysis will be covered in the analysis in Section 5.5.2.4.

5.5.2.4. Change From Baseline in the MG-ADL Total Score at Week 26 for Groups 1 and 2 and From Weeks 8 to 34 for Groups 3a and 3b

This analysis includes MG-ADL data of first 8 weeks (Group 1, 2, and 3) and Week 8 to 34 data for Group 1, 2, 3a, and 3b participants.

Change from Baseline in the MG-ADL total score at Week 26 for Groups 1 and 2 and change from Baseline in the MG-ADL total score at Week 34 for Group 3a and 3b will be summarized. Change from Baseline in the MG-ADL total score by study visit up to Week 34 and treatment group will be summarized.

Summaries using the PEP and ETP baselines will be both presented for Groups 3a and 3b.

